Study Protocol

1. Background

Research on the relationship between biomarkers in human cerebrospinal fluid (CSF) and aging is a current hotspot in the field of neuroscience. Analyzing specific proteins and other molecules in CSF can provide important information for the early diagnosis and pathological progression of neurodegenerative diseases. Common biomarkers in CSF include amyloid-beta (Aβ42) and phosphorylated tau protein (p-tau181)1. The concentration changes of these markers have significant diagnostic value in Alzheimer's disease (AD) and other neurodegenerative diseases. A decrease in Aβ42 levels and an increase in p-tau181 levels are closely associated with the pathological features of AD2. Aging is a major risk factor for neurodegenerative diseases, and studies have found that the levels of $A\beta$ and tau proteins in CSF undergo significant changes with increasing age. These changes are particularly evident in neurodegenerative diseases such as Alzheimer's disease and Lewy body dementia3. Research shows that monitoring biomarkers in CSF can aid in the early identification of these diseases, thereby facilitating early intervention and treatment4. Modern studies utilizing high-throughput proteomics and other advanced biotechnologies have revealed many new potential biomarkers in CSF. For example, mass spectrometry can detect protein changes related to neuroinflammation and blood-brain barrier function, which are crucial for understanding the neurodegenerative pathological mechanisms during aging5.

In-depth research into CSF biomarkers not only aids in understanding the neurodegenerative changes during aging but also promotes the development of early diagnostic techniques, improving the management and treatment of neurological diseases in the elderly population. Future research will further explore the mechanisms and applications of these biomarkers, aiming to achieve broader and more precise diagnosis in clinical practice.

References:

associated with aberrant cerebrospinal fluid p-tau181 and A β 42 in Alzheimer's disease and other neurodegenerative diseases. Acta Neuropathol Commun. 2024;12(1):48. Published 2024 Mar 27. doi:10.1186/s40478-024-01758-3

- 3. O'Leary K. A timeline of biomarker changes before Alzheimer's disease. Nat Med. Published online March 15, 2024. doi:10.1038/d41591-024-00018-0

2. Objective

Analyzing CSF samples from different age groups to identify biomarkers that undergo significant changes during the aging process, such as amyloid-beta ($A\beta42$), tau protein (including its phosphorylated form, p-tau181), and other proteins related to neuroinflammation and blood-brain barrier function.

Establishing a predictive model through the analysis of CSF protein levels and classification across different age stages, to enable the early diagnosis of neurodegenerative diseases (e.g., Alzheimer's disease). This could allow for the detection of diseases before clinical symptoms appear, providing the possibility for early intervention and treatment.

Investigating the dynamic changes of CSF biomarkers at different stages of disease to understand their roles in disease progression, including changes in the early, middle, and late stages. This will help to better understand the pathological process and identify potential

therapeutic windows.

Creating a database of CSF biomarkers that encompasses different age groups, disease states, and treatment responses. This database will provide valuable data resources for future research, facilitating the scientific community's understanding of neurodegenerative diseases and the development of new therapies.

Through the achievement of these objectives, this study aims to advance the development of CSF biomarkers in neuroscience research and clinical applications, improving the diagnosis, management, and treatment of aging and neurodegenerative diseases.

3. Method

Prospective Collection of Cerebrospinal Fluid from Patients Aged 0-90 Years Without Neurological Diseases:

Study Duration: 1 year, starting from the date of ethical approval and ending 1 calendar year after the date of ethical approval.

Inclusion Criteria:

Patients aged 0-90 years.

Patients admitted for surgery under spinal anesthesia due to non-neurological conditions such as lower limb fractures, hemorrhoids, etc.

Pediatric patients requiring surgery for tethered cord syndrome.

Exclusion Criteria: Patients with neurological diseases, including but not limited to encephalitis, Parkinson's disease, Alzheimer's disease, hydrocephalus, brain tumors, and psychiatric disorders.

Withdrawal Criteria: Participants may voluntarily withdraw from the study at any time for any reason.

Specific Research Protocol:

Data Collection: Clinical data will be collected, including the patient's name, gender, age, and primary diagnosis. This information will be sourced from the hospital admission case system.

Cerebrospinal Fluid (CSF) Collection:

During spinal anesthesia, CSF is withdrawn to confirm the correct placement in the subarachnoid space before administering the anesthetic, with approximately 1-2 mL of CSF retained.

During surgery for tethered cord syndrome, 2 mL of CSF is collected before opening the dura mater.

The collected CSF is placed in a 0°C insulated container for storage and transportation, then centrifuged in the laboratory and stored at -80°C until further analysis.

After the collection is complete, multi-omics analyses, including proteomics and metabolomics, will be conducted.

Proteomics Analysis:

Sample Preparation:

100 µL of CSF is mixed with high-abundance protein depletion resin to enhance proteome depth, incubated at room temperature for 20 minutes, and the eluate is collected.

The sample is concentrated using a 3k molecular weight cutoff protein concentrator at 12,000 g for 30 minutes and exchanged with lysis buffer (8M urea) for protein denaturation.

After centrifugation at 12,000 g, less than 50 µL of solution remains in the tube.

The concentrated sample is reduced with 10 mM tris(2-carboxyethyl)phosphine hydrochloride at 32°C for 40 minutes, followed by alkylation with 40 mM iodoacetamide at room temperature in the dark for 30 minutes.

CSF samples are digested in two steps using 2.5 $\,\mu g$ of endoproteinase and 2.5 $\,\mu g$ of trypsin for 12 hours.

The peptides are acidified with trifluoroacetic acid, desalted using a 2 mg liquid-phase ion exchange column, and the eluate is dried using a vacuum concentrator.

Each batch is labeled with 56 μg of TMT16plex reagent for peptides from each sample. After 1-hour incubation at room temperature, TMT labeling is quenched with

hydroxylamine, and 16 samples from a batch are pooled and fractionated using a C18 column.

Fractions are separated into 96 fractions with a gradient from 5% to 35% acetonitrile in 10 mM ammonia water at a flow rate of 1 mL/min. The first to seventh, 37th, and 67th fractions are pooled, and the remaining fractions are evenly pooled and vacuum dried.

The dried peptide powder is reconstituted in 2% acetonitrile/0.1% formic acid and analyzed by LC-MS/MS.

Data Analysis:

MS raw data is searched against the human protein fasta file downloaded from UniProtKB14, which contains 20,394 protein entries.

The parent ion mass tolerance is set to 10 ppm, and the fragment ion mass tolerance is set to 0.02 Da.

Subsequent statistical analysis is performed by comparing the abundance ratios of samples within the same batch to the combined sample.

Bioinformatics software is used to analyze the mass spectrometry data, including protein identification, quantification, and differential analysis.

4. sample capacity

Participants will be divided into 9 groups based on age, with each group covering a 10-year range (1-10 years, 11-20 years, etc.), totaling 9 groups. Each group will include 10-15 participants, with a planned total enrollment of 100-150 cases.

5. Data management and confidentiality

Data Entry and Modification:

Data entry and management will be handled by [name] and [name]. To ensure accuracy, two data administrators will independently enter and cross-check the data.

Database Locking:

Once the database has been confirmed to be accurate, it will be locked by the principal investigator and statistical analysts. All records related to participant identities will be kept confidential and will not be disclosed outside the scope allowed by relevant laws and/or First edition 2024-06-27

regulations.

6. informed consent

Before the clinical study begins, the researchers must provide detailed information to the participants or their legal guardians, including the nature of the study, its purpose, potential benefits, and risks. This ensures that participants or their legal guardians fully understand the clinical study. The clinical study can only commence after the informed consent form has been signed.

Each patient must provide detailed contact information, including their address and phone number. Additionally, the researcher will sign the informed consent form with the patient before the surgery and provide the patient with their contact information so that the patient can reach the researcher at any time.

7. Adverse Event Reporting

This study involves the collection of 1-2 mL of cerebrospinal fluid (CSF) under spinal anesthesia. A very small number of patients may experience headaches or discomfort after the procedure, which can be alleviated by increasing fluid intake.

General Adverse Events: Timely measures will be taken to address any adverse events, and they will be recorded in the case report form.

Serious Adverse Events (SAE): Timely measures will be taken to address any SAE. The event will be recorded in the case report form, and the researcher will decide whether to stop or reduce treatment. The SAE must be reported immediately to the Ethics Committee, the drug clinical trial institution, and the sponsor. Additionally, within 24 hours, it must be reported to the National and Provincial Food and Drug Administration. The SAE must also be reported through the "Internal Adverse Event and Near-Miss No-Fault Reporting System." For the detailed process, see the diagram below.

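### Does the first objective fail because the described workflow states no read-out for Aβ42 and p-tau181?

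*Protocol*

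**What the plan says.** Section 2 of the protocol (Objective) opens with a discovery aim: compare CSF across age groups and find the biomarkers that change. Aβ42 and tau are offered as examples, the second worded "tau protein (including its phosphorylated form, p-tau181" before the bracket closes. The list then moves on to other proteins linked to neuroinflammation and blood-brain barrier function. Section 1 (Background) gives the clinical context for the two forms, saying for the second that "an increase in p-tau181 levels are closely associated with the pathological features of AD2" (the final digit is a reference number).

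Section 3 (Method) says that after collection "multi-omics analyses, including proteomics and metabolomics, will be conducted". Only the proteomics workflow is then described. From 100 µL of CSF, high-abundance proteins are depleted, the sample is concentrated, reduced and alkylated, and "CSF samples are digested in two steps". The peptides are labelled with TMT16plex, fractionated and run on LC-MS/MS. For the search, the Data Analysis part of Section 3 states: "MS raw data is searched against the human protein fasta file downloaded from UniProtKB14, which contains 20,394 protein entries". It adds: "The parent ion mass tolerance is set to 10 ppm, and the fragment ion mass tolerance is set to 0.02 Da". The statistical comparison is made by "comparing the abundance ratios of samples within the same batch to the combined sample", and the software step is described as "including protein identification, quantification, and differential analysis".

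Aβ42 and p-tau181 are not mentioned anywhere in Section 3.

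**The concern.** Aβ42 is defined by its length and p-tau181 by a phosphorylated site. A workflow that digests the sample and sums peptides to a protein ratio naturally reports the precursor of Aβ and total tau, not these two forms. Measuring them would ordinarily take an immunoassay, a targeted mass-spectrometry assay, phosphopeptide enrichment, or a search that allows for the modification and for non-standard cleavage. Section 3 states none of these, although it is detailed elsewhere, down to reagent masses and incubation times.

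If the study could say nothing about the two best-known markers in its own rationale, an objective and its method would not match. A precursor or total-tau ratio might also be labelled as Aβ42 or p-tau181 in the predictive model or the database that Section 2 plans. Choosing an assay is a laboratory decision, so a statistical analysis plan could not repair the gap later.

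**Working it through.** The protocol states no figure on this point, so the check is mainly a comparison of texts, with two counts and one volume calculation.

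**1. What is named and what is specifically provided for.** The first objective names 3 specific molecules: Aβ42, tau and p-tau181. Steps, settings or assays in Section 3 specific to Aβ42: 0. Specific to p-tau181: 0. If total tau is taken as covered by ordinary protein quantification, 2 of 3 lack a stated read-out. However, no step is specific to tau either, and nothing states that tau will be detected. Under the strict test of a named step, the count becomes 3 of 3. A count that moves with the test chosen shows how brief the description is. It does not show that a measurement fails.

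**2. Whether silence on search settings is informative.** Data Analysis states 3 search inputs: the fasta file, 10 ppm and 0.02 Da. Sample Preparation describes three things that a search of these data has to account for:

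| Described in Sample Preparation | Listed as a search setting in Data Analysis |
|---|---|
| Alkylation with iodoacetamide | No |
| TMT16plex label | No |
| Digestion with endoproteinase and trypsin | No |

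If an unlisted setting meant an unused setting, the protocol's own label would go unsearched, which cannot be intended. The list is therefore incomplete, and the absence of a phosphorylation or cleavage setting is weak evidence that none will be used.

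**3. Whether the list of analyses is closed.** It is not: "multi-omics analyses, including proteomics and metabolomics, will be conducted" uses an inclusive term. Metabolomics is certainly planned, yet has no workflow at all. In this document an undescribed analysis is not an excluded one. The same holds for the software step, which is also worded inclusively.

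**4. What depends on the two forms.** They are examples and not endpoints. Section 4 sets the sample size as a number of participants per age group, without reference to any marker. The statistical comparison is a ratio to the combined sample for whatever is quantified. Removing both names from the objective would alter none of these.

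**5. Whether CSF volume rules out a separate assay.** Proteomics uses 100 µL = 0.1 mL. Spinal-anaesthesia samples are 1–2 mL and tethered-cord samples 2 mL.
- Share used: 0.1/2 = 5%; 0.1/1 = 10%.
- Left before metabolomics and handling losses: 1.0 − 0.1 = 0.9 mL; 2.0 − 0.1 = 1.9 mL.
- The metabolomics volume is not stated. At an assumed 0.1–0.5 mL, the lowest remainder is 0.9 − 0.5 = 0.4 mL and the highest is 1.9 − 0.1 = 1.8 mL.

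The volumes do not close off a later assay. They bear on feasibility only.

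**The case for a change.** The strongest case for a change is that the protocol is precise about the bench work, so silence on two named markers reads as a mismatch and not as brevity. Being introduced as examples does not excuse them, because a named example ought to be measurable by the stated method. An open list of analyses names no assay. The remedy would also be cheap: a few words in the objective, or one sentence naming the assay.

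Part of this stands. Section 3 does not say how, or whether, the two forms will be measured, and a reader may fairly ask. Reading the stated output as protein-level is also reasonable, although the protocol does not use that term.

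The stronger conclusion, that the study will have no valid result for either form, does not stand. It needs the settings list and the list of analyses to be complete, and neither is. The dependence on the two markers is also easy to overstate. The Background argues equally that high-throughput proteomics has yielded new candidate markers and that mass spectrometry detects inflammatory and barrier-related proteins, which is the work Section 3 describes. The mislabelling risk is speculative: nothing in the protocol suggests that a precursor or total-tau ratio would be reported as Aβ42 or p-tau181, and the lack of a rule against it is not an error.

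**Conclusion.** No change to the plan is called for. The protocol leaves out a detail: it does not describe how Aβ42 and p-tau181 would be measured. Analysts can handle this sensibly by reporting each quantity as what was actually measured, so that a protein ratio for tau is called total tau. Carried out as written, the age-related discovery analysis and its conclusions remain sound.

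The gap concerns 2 of the 3 specifically named molecules, both illustrative, and touches no endpoint, sample size or stated figure. The possible edits gain little. Rewording the objective changes no result, and naming an assay already intended only records a detail. Adding a new assay would need further resources for markers that the discovery aim does not depend on. Reserving an aliquot protects little when proteomics takes 5–10% of the sample.

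This rests on two readings: that the two forms are examples and not committed targets, and that the stated search inputs are a partial list. If the sponsor treated either form as a required result, its measurement would have to be specified before the samples are processed. Nothing in the protocol says so.

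### Tethered cord children enter a cohort defined as free of neurological disease with no written exception, and their diagnosis and collection setting can pass for an age effect in the pediatric groups

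*Protocol*

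**What the plan says.** The cohort heading in protocol section 3 (Method) reads "Prospective Collection of Cerebrospinal Fluid from Patients Aged 0-90 Years Without Neurological Diseases". Two inclusion routes follow:

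- **Spinal anesthesia route:** "Patients admitted for surgery under spinal anesthesia due to non-neurological conditions such as lower limb fractures, hemorrhoids, etc".
- **Tethered cord route:** "Pediatric patients requiring surgery for tethered cord syndrome".

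The exclusion begins "Exclusion Criteria: Patients with neurological diseases, including but not limited to encephalitis" and continues with further examples. Tethered cord syndrome is not among them, but the list is open-ended and no exception is written.

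CSF collection also differs by route. For most participants, "During spinal anesthesia, CSF is withdrawn to confirm the correct placement in the subarachnoid space before administering the anesthetic". For the children on the second route, "During surgery for tethered cord syndrome, 2 mL of CSF is collected before opening the dura mater".

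The first objective (section 2) is "Analyzing CSF samples from different age groups to identify biomarkers that undergo significant changes during the aging process". Section 4 plans nine ten-year age groups of 10-15 participants, starting with ages 1-10 and 11-20. The clinical data collected include "gender, age, and primary diagnosis".

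**The concern.** There are two linked problems.

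First, one clause admits these children, while the cohort definition and the general exclusion, read literally, keep out anyone with a neurological disease. Tethered cord syndrome concerns the spinal cord, and the protocol lists it apart from its non-neurological surgical conditions. A reader of the results or of the planned database could take these samples as coming from people free of neurological disease.

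Second, source is tied to age. The tethered cord route is pediatric only, and it brings both a different diagnosis and a different collection setting. If either changes a protein's level, that change enters the mean of any age group containing these children and looks like aging. At stake are the early-life contrasts of the first objective, in groups of only 10-15 people.

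**Working it through.** **The text.** The cohort definition and the exclusion carry no exception. The inclusion line and the collection step provide for these children. Both can hold only if an exception is read in, so the eligibility text is unreconciled but its intent can be inferred.

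**Reach.** With groups 1-10, 11-20 and so on, and taking pediatric to end by age 20, at most 2 of 9 groups can contain these children: 20-30 participants at 10-15 per group.

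**Size.** The protocol has no figure to reproduce here: no tethered cord share, source effect, SD or test. The following is illustration only. *Assumptions:* SD 1, no true age effect, a source shift d of 0.5 or 1.0 SD, no adjustment, and a two-sided 5% t test of one pediatric group against one group of equal size without these children. If k of n in the group are tethered cord, its mean moves by (k/n) × d; for 5 of 10 and d = 1, that is 0.5 × 1 = 0.50 SD. Rejection rates come from simulation (200,000 replicates) for mixed groups and from the exact noncentral t for groups wholly tethered cord.

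| Tethered cord in group | Mean shift, d = 0.5 / 1.0 | Rejection rate, d = 0.5 / 1.0 |
|---|---|---|
| 5 of 10 | 0.25 / 0.50 | 0.078 / 0.154 |
| 7 of 15 | 0.23 / 0.47 | 0.090 / 0.199 |
| 8 of 15 | 0.27 / 0.53 | 0.102 / 0.251 |
| 10 of 10 | 0.50 / 1.00 | 0.185 / 0.562 |
| 15 of 15 | 0.50 / 1.00 | 0.262 / 0.753 |

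With a quarter of the group and d = 0.5, a normal approximation gives about 0.06. With no source effect, or none of these children, the rate is 0.05.

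**Can adjustment separate source from age?**

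- *Age-group indicators, one group all tethered cord.* Nine group indicators plus a source indicator have rank 9 for 10 columns, so source and age cannot be separated for that group.
- *Age-group indicators, one mixed group.* The source-adjusted contrast equals the contrast with these children left out. The source effect itself has SE √(1/5 + 1/5) = 0.63 for 5 against 5, or √(1/7 + 1/8) = 0.52 for 7 against 8. With pooled variance the 95% half-widths are 1.26 and 1.02 SD.
- *Linear age model with a source term.* Take a real 1 SD change confined to the first decade, no source effect, and groups placed at x = 1 to 9. With everyone included and no source term, at n = 10 the slope has absolute size 10 × 4 × 1 / (10 × 60) = 0.0667 per decade. With 5 of 10 tethered cord and a source term, it falls to 0.0411, a loss of 1 − 0.0411/0.0667 = 38%, and the source term takes a spurious 0.77 SD. For 7 of 15 and 8 of 15 the losses are 35% and 42%, with spurious source effects of 0.76 and 0.78 SD. If the whole group is tethered cord, the loss is 100%. Fitting the line without these children gives the same reduced slopes.

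**Cost in power.** For a true 1 SD difference between the youngest and one other group, leaving out half of the youngest group changes exact power as follows: 10 v 10 to 5 v 10, 0.562 to 0.394; 15 v 15 to 8 v 15 or 7 v 15, 0.753 to 0.587 or 0.547.

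**The case against.** The strongest reply is that a specific inclusion line beside a general exclusion is naturally read as an exception. The protocol never classifies tethered cord syndrome as neurological, its named exclusions omit it, and it gives these children their own collection step. This largely stands: a reader might infer a flat contradiction, and the text does not support that. What remains is that the exception has to be inferred while the cohort heading says the opposite.

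A second reply is that adjustment and sensitivity analyses usually belong to the statistical analysis plan, which is not shown, and that the recorded primary diagnosis leaves both open. That is fair, so their absence is not held against the protocol. Nor are a definition of pediatric or expected numbers per group. Eligibility, cohort label and recruitment route are protocol matters, however, and analysis cannot separate source from age in a group made up of one source.

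A third reply is that no source effect is shown. This is correct: shift and share are assumed, and with a small share and a modest shift the rejection rate is close to 5%. A reader might also infer that the youngest group will consist only of tethered cord children. The protocol does not say so; children can also enter through spinal anesthesia. It does not prevent it either.

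It is also tempting to say that the other age groups are untouched. The Data Analysis text in section 3 compares samples with a combined sample within each batch. If that reference contains tethered cord samples in some batches and not in others, ratios for other participants could shift too.

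**Conclusion.** The point holds in a limited form and should be fixed. The eligibility wording needs reconciling. Source is confounded with age in any pediatric group containing these children, fully if the group contains no one else. The size cannot be derived from the protocol. Under the assumed 0.5-1.0 SD shift with no adjustment, the false-positive rate for one comparison runs from about 8% (half the group, small shift) to 75% (all of a group of 15, large shift). The upper figures depend on a group composition that the protocol does not state.

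The documents do not support a conclusion that the age analysis as a whole is invalid: at most two of nine groups are directly involved, and bias arises only for proteins that respond to the diagnosis or the collection setting. Confidence is medium.

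**What to change.** 1. Reconcile the cohort definition, inclusion and exclusion text in section 3.
2. If the children are kept, label them as a separate source stratum, derived from the recorded primary diagnosis, and do not describe them as free of neurological disease in the analysis or the database.
3. Report age-group results with and without them. Where a group contains both sources, compare by age-group indicators and give source-adjusted contrasts with their precision.
4. Do not rely on a source term in a linear age model, whether the group is mixed or all tethered cord, because it can absorb a real early-life change. A linear slope fitted without these children is attenuated in the same way, so its fall is not by itself evidence of a source effect.
5. Do not attribute to age a difference that rests on a group made up only of these children.
6. Do not state that other groups are unaffected unless the combined reference sample has the same composition across batches.

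The cost is protocol wording, one variable derived from data already collected, and one added analysis. The results without these children have less power at the youngest ages: with half the group left out, 56% falls to 39% at 10 per group, or 75% to 55-59% at 15 per group, for a true 1 SD difference. If a group is all tethered cord, the analysis without them says nothing about that age range. Early-life claims become more cautious.

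### Does an eligible infant under 1 year fall outside the nine age groups?

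*Protocol*

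**What the plan says.** Section 3 (Method) opens by describing collection from "Patients Aged 0-90 Years" without neurological disease, and the first inclusion criterion repeats that age range. A further inclusion criterion admits "Pediatric patients requiring surgery for tethered cord syndrome" and sets no minimum age of its own, so the only floor for these children is the general one of 0.

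Section 4 (sample capacity) states "Participants will be divided into 9 groups based on age" and describes the bands as "each group covering a 10-year range (1-10 years, 11-20 years, etc.), totaling 9 groups". It then sets the numbers: "Each group will include 10-15 participants, with a planned total enrollment of 100-150 cases".

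The first aim in section 2 (Objective) is "Analyzing CSF samples from different age groups to identify biomarkers that undergo significant changes during the aging process". It does not name the nine bands. The Data Analysis part of section 3 describes comparing each sample's abundance ratios with the combined sample of its batch, and does not mention age bands. Age is one of the clinical variables taken from the hospital admission system.

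**The concern.** The eligibility range starts at 0 and the first age band starts at 1. Read literally, a child of a few months meets the age criterion and can enter through the tethered cord route, yet has no band among the nine. Because section 4 attaches a quota of 10-15 to each band, the child would also count towards no quota.

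Two things would be at stake. During recruitment, staff need to know which band a participant fills. At analysis, a participant who consented and gave CSF could be placed inconsistently or dropped from a comparison by age group. With groups this small, a few such participants could be visible. As an illustration only, since the protocol gives no expected number, 2 infants would be 2/15 = 13% to 2/10 = 20% of a group of 10-15.

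**Working it through.** No power formula applies. The check is to list the bands and see which eligible ages they cover.

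**Inputs.** Eligible age 0-90 years (section 3). Nine bands of 10 years, the first two given as 1-10 and 11-20 (section 4). Quota 10-15 per band (section 4).

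**The protocol's own count.** Continuing the pattern gives 1-10, 11-20, 21-30, 31-40, 41-50, 51-60, 61-70, 71-80 and 81-90. That is nine bands, as stated.

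**Reading 1: completed years for both eligibility and bands.**
- Eligible ages: 0, 1, ..., 90, which is 91 values.
- Ages in bands: 9 x 10 = 90 values, 1 to 90.
- Left over: 91 - 90 = 1 value, age 0.

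**Reading 2: bands as years of life (first to tenth, eleventh to twentieth, and so on).**
- The bands run from birth up to the 90th birthday, which is 9 x 10 = 90 years.
- An infant under 1 is in the first year of life and so in the first band.
- If 0-90 means from birth to the 90th birthday, eligibility also spans 90 - 0 = 90 years, and nine bands of 10 years fill it exactly, apart from the boundary point.
- If 0-90 also takes in people who have passed their 90th birthday but not their 91st, those people are outside the last band.

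The infant is therefore without a band on reading 1 only. On reading 2 the sole possible gap is at age 90, and it depends on how the upper limit of eligibility is understood. The protocol settles neither point.

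**What the gap does on reading 1.** Age 0 adjoins one band, 1-10; the next starts at 11. Placing infants in the first band makes it 0-10, or 11 completed years, with 10 in each of the other eight: 11 + 8 x 10 = 91. Every eligible age then has exactly one group and the number of groups stays at nine.

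**What an amendment would add.** Compare two cases: the label stays 1-10 and infants are put in the nearest band, or the label is amended to 0-10. The same participants sit in the same nine groups in both. Any comparison between groups gives the same result, and an analysis of age as a continuous variable does not use the bands at all.

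**The case for a change.** The strongest case for acting is that the protocol itself fixes the groups and ties recruitment quotas to them, so this is not a detail that can wait for the analysis plan. A range starting at 0 suggests that age is counted from 0, so reading the bands as years of life means section 4 uses a different convention from section 3 without saying so. The tethered cord route makes infants a real possibility, and the cure is one sentence.

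Much of this stands. The two sections do not match word for word, infants are eligible, and the year-of-life reading is nowhere stated. What does not stand is the step from there to a consequence. The bands are sketched in a parenthesis that trails off in an abbreviation, in the section on numbers, and nothing makes those exact cut-points the analysis factor. Exclusion of an infant from the group comparison is conjecture: the protocol contains no rule that would exclude one, and the placement is obvious. Staff could differ only if there were two plausible bands, and there is one. Age is recorded for everyone, so any assignment can be checked later. If infants differ from older children in the first band, relabelling it would not separate them.

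A separate group for infants under 1 would be a different design. It would make ten groups, and 10 x 10 to 10 x 15 is 100 to 150, which equals the stated total, whereas nine groups give 9 x 10 = 90 to 9 x 15 = 135. That mismatch of totals is its own question. It does not show that a tenth group was meant, because section 4 gives the number as nine twice.

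**Conclusion.** This is a clerical mismatch between an eligibility range and an abbreviated list of bands, and it does not call for a change to the plan. On the completed-years reading it affects one age, 0. On the year-of-life reading it does not affect infants. In either case the sensible placement is the first band, and using it leaves the nine groups and their quotas as planned, with no effect on bias, power or conclusions.

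This rests on two assumptions: that the pattern of bands runs on to 81-90, and that whoever assigns groups puts an infant in the only adjacent band. The number of infants is not given, so the share of participants touched cannot be stated and may be nil. If the text is ever edited for other reasons, the sponsor could align it from either side, by widening the label of the first band or by starting eligibility at 1. The first would leave the grouping as it would be anyway; the second would alter who is eligible and is the sponsor's choice. Neither is needed for the study to be analysed properly.
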